### 7.3 Subject Disposition

The number and percentage of subjects who completed assessments (complete assessments up to Day 8 and complete assessment up to Day 90) and discontinued prematurely by reason will be summarized separately for the Efficacy Population and the Safety Population, by the icatibant exposure number. For the initial icatibant exposure, the analyses will be presented by the pubertal status and overall; for the subsequent icatibant exposures, the analyses will be presented by the administration type (HCP Administration vs. Caregiver Administration) and overall.

The number and percentage of subjects who completed assessments and discontinued prematurely by reason will be summarized separately for the Efficacy Population and the Safety Population by pubertal status stratification level.

### 7.4 Demographics and Pre-treatment Characteristics

Demographic and pre-treatment characteristics (age at screening [years], age at exposure [years], age group at exposure [<6 years, 6-11 years, >11 years], sex [male, female], race [American Indian or Alaskan Native, Asian, Black or African American, Native Hawaiian or other Pacific Islander, White, Other], ethnicity [Hispanic or Latino, Not Hispanic or Latino], weight at exposure [kg], weight group at exposure [<75 kg, ≥75 kg], weight percentile at exposure, height at exposure [cm], height percentile at exposure [cm], BMI [kg/m^2] at exposure, BMI percentile at exposure, and country) will be summarized separately for the Efficacy Population and the Safety Population, and by icatibant exposure number. For the initial icatibant exposure, the analyses will be presented by the pubertal status and overall; for the subsequent icatibant exposures, the analyses will be presented by the administration type (HCP Administration vs. Caregiver Administration) and overall.

### 7.5 Medical and HAE History

Medical history will be coded using the Medical Dictionary for Regulatory Activities (MedDRA) version 16.0 and summarized by system organ class (SOC) and preferred term (PT) for the Efficacy Population and the Safety Population, and by icatibant exposure number. For the initial icatibant exposure, the analyses will be presented by the pubertal status and overall; for the subsequent icatibant exposures, the analyses will be presented by the administration type (HCP Administration vs. Caregiver Administration) and overall.

History of HAE (family history [yes, no], time since diagnosis at first treatment [years], type of last attack [cutaneous, abdominal, cutaneous and abdominal, or laryngeal], and time since last attack at first treatment [months]) and details on previous HAE attacks (number of attacks in last 12 months, average duration of attacks [days], average time between onset of symptoms and relief [days], and most frequent severity of attacks [mild, moderate, or severe]) for each attack type (cutaneous, abdominal, cutaneous and abdominal, and laryngeal) will be summarized separately for the Efficacy Population and the Safety Population, and by icatibant exposure number. For the initial icatibant exposure, the analyses will be presented by the pubertal status and overall; for the subsequent icatibant exposures, the analyses will be presented by the administration type (HCP Administration vs. Caregiver Administration) and overall.

Medical history and HAE history will also be provided in listings.

### 7.6 On-Study HAE Attacks and Drug Exposure

Type of attack (cutaneous, abdominal, laryngeal) and time from attack onset to study drug administration (hours) will be summarized for the Efficacy Population, by icatibant exposure number. For the initial icatibant exposure, the analyses will be presented by the pubertal status and overall; for the subsequent icatibant exposures, the analyses will be presented by the administration type (HCP Administration vs. Caregiver Administration) and overall.

Number of injections will be summarized for the Efficacy Population and Safety Population, by icatibant exposure number. For the initial icatibant exposure, the analyses will be presented by the pubertal status and overall; for the subsequent icatibant exposures, the analyses will be presented by the administration type (HCP Administration vs. Caregiver Administration) and overall.

The exposure information for all icatibant administrations given as part of the study will also be presented in a listing.

### 7.7 Protocol Deviations

Prior to the interim data cut, protocol deviations will be reviewed by the study team and the subset of protocol deviations that may have significantly impacted the completeness, accuracy, and/or reliability of the study data or that may significantly affected a subject's rights, safety, or well-being will be identified as significant protocol deviations.

A listing of the protocol deviations will be provided for each subject.

### 7.8 Efficacy Analysis

Efficacy will be assessed using data from the investigator symptom score, FPS-R and FLACC. The corresponding analyses will be based on the Efficacy Population. All efficacy summaries will be presented by icatibant exposure number. For the initial icatibant exposure, the analyses will be presented by the pubertal status and overall; for the subsequent icatibant exposures, the analyses will be presented by the administration type (HCP Administration vs. Caregiver Administration) and overall.

All efficacy results will be listed by subject.

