8.4.2 Treatment Period (Day 1 to Day 8 [± 1 Day])

8.4.2.1 Day of Subsequent Attack (Day 1)

When a pubertal/postpubertal subject experiences an acute HAE attack, subjects (parent/legal guardian/caregiver) will contact the hospital/study center (or their home healthcare professional in the event the investigator is not available) to confirm the HAE attack diagnosis.

The investigator (or the home healthcare professional in the event the investigator is not available), in consultation with the subject's preference, will determine whether the subject will be treated at the hospital/study center, at home by a qualified home healthcare personnel, at home by the trained parent/legal guardian/caregiver, or by self-administration. The qualified home healthcare person will be contacted, if applicable.

The following will occur prior to study drug administration:

	Subject Treated at Study Site	Subject Treated at Home
Call hospital/study center (or their home healthcare professional in the event the investigator is not available) to confirm the HAE attack diagnosis	X	X
Investigator Symptom Score	X	
Home Healthcare Provide or Parent/Legal Guardian/Caregiver Symptom Score	X	X
Subject Self-Assessment of Pain	X	X
Urine pregnancy test	X	X
Concomitant Medications	X	X
Adverse Events	X	X

- Assessment of HAE symptoms
 - The investigator will assess HAE symptoms using the Investigator Symptom Score if the subject is treated at the hospital/study center
 - The home healthcare provider will assess HAE symptoms using the Home Healthcare Provider or Parent/Legal Guardian/Caregiver Symptom Score if the subject is treated at home
 - The parent/legal guardian/caregiver will assess HAE symptoms using the Home Healthcare Provider or Parent/Legal Guardian/Caregiver Symptom Score if the subject is treated at either the hospital/study site or at home
- Subject will self-assess HAE-related pain using diary FPS-R
- Urine pregnancy test for females of child-bearing potential
- Concomitant medications will be recorded
- Adverse events will be recorded

Once the pretreatment assessments are completed, icatibant will be administered (Day 1, Time 0).

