Two subsets of subjects, those 4 years of age or older and those below 4 years of age, will have assessment of pain using the FPS-R and FLACC instruments, respectively. For subjects ≥ 4 years of age, the time to onset of symptom relief is defined as the earliest time at which the post-treatment score improves by at least one level. The time to onset of symptom relief for subjects < 4 years of age is defined as the earliest time at which a 20% improvement is seen in the total post-treatment score. Additionally, time to minimal symptoms defined as the earliest time at

which the post-treatment score (or total post-treatment score for FLACC) improves to zero, will be analyzed. The time to onset of symptom relief and time to minimal symptoms will be analyzed using the same methods as the primary efficacy endpoint.

Home healthcare provider or parent/legal guardian/caregiver symptom scores (referred to as caregiver-reported symptom scores hereafter) will be measured for all subjects' subsequent icatibant-treated attacks. A tabular summary of the average caregiver-reported symptom scores and the change from baseline in the average caregiver-reported symptom scores will be presented by the stratification group and the subsequent icatibant treated attack number. For individual caregiver-reported symptom scores, a shift table from baseline will be presented for each post-treatment time point.

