### 7.2 Analysis Populations

The following populations will be used in the analysis:

- The Efficacy Population will consist of those subjects who were treated with icatibant for their first and any additional attacks during the study.
- The Safety Population will consist of those subjects who were treated with icatibant at least once during the study (irrespective of the presence of an HAE attack).

All efficacy analyses will be performed on the Efficacy Population. The corresponding tabular summaries will be presented by the icatibant exposure number. For the initial icatibant exposure, the analyses will be presented by the pubertal status (Pre-pubertal vs. Pubertal/Post-pubertal) and overall; for the subsequent icatibant exposures, the analyses will be presented by the administration type (Study Site Personnel (HCP Administration) vs. Home Healthcare Providers/Patient/Parent/Legal Guardian/Caregiver (Caregiver Administration)) and overall.

Safety and tolerability analyses will be based on the Safety Population. All tabular summaries within this population will be presented by the icatibant exposure number. For the initial icatibant exposure, the analyses will be presented by the pubertal status (Pre-pubertal vs. Pubertal/Post-pubertal) and overall; for the subsequent icatibant exposures, the analyses will be presented by the administration type (HCP Administration vs. Caregiver Administration) and overall.

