## 10.3.3 Study Schedule of Events (Subsequent Icatibant-treated Attacks)

	Subsequent Icatibant-Treated Attack Baseline a (Site)	Every Month after Baseline (Home) b	Treatment					Post Treatment	
			Prior to Dosing	Day 1 (Site or Home)			Day 2 (Home)	Day 8 ( $\pm 1$ ) c (Site)	Day 90 ( $\pm 7$ ) c (Site)
				0	1	2	6-8	24	
Time Post Treatment (hours)									
Window (hours or minutes)				( $\pm 10$ ) min	( $\pm 10$ ) min	( $\pm 4$ ) hr	( $\pm 4$ ) hr		
Assessments									
Inclusion/Exclusion Assessment	X	X							
Menstrual Cycle History	X								X
Documentation of HAE Attack(s) Not Treated with icatibant	X	X							X
Physical Examination	X								X
Vital Signs	X							X	X
Height and Weight	X								X
Clinical Laboratory Tests (serum chemistry/hematology)	X								X
Urine Pregnancy Test (in females of childbearing potential)	X		X						X
Reproductive Hormone Assessments (FSH, LH, estradiol, progesterone in females; FSH, LH, testosterone in males)	X							X	X
Immunogenicity Evaluation	X							X	X
Training on icatibant administration d	X								
Training on how to assess HAE symptoms, time to initial symptom relief, and injection site reactions d	X								
Dispense 1 syringe of icatibant d	X								
Contact investigator with weight to confirm dose d		X							
Contact investigator in the event of an HAE attack			X b						
Investigational Product Administration (single SC dose)				X c					
Subject Self-assessment of HAE-related Pain Using FPS-R			X	X	X f	X f	X		
Investigator Assessment of HAE Symptoms			X g	X g,h	X g,h	X g,h			

	Subsequent Icatibant-Treated Attack Baseline a (Site)	Every Month after Baseline (Home) b	Treatment						Post Treatment	
			Prior to Dosing	Day 1 (Site or Home)			Day 2 (Home)	Day 8 (±1) c (Site)	Day 90 (±7) c (Site)	
Time Post Treatment (hours)				0	1	2	6-8	24		
Window (hours or minutes)					(±10) min	(±10) min	(±4) hr	(±4) hr		
Assessments										
Home Healthcare Provider or Parent/Legal Guardian/Caregiver Assessment of HAE Symptoms			X		X h	X h	X h			
Record Injection Site Reactions					X b, i	X b, i	X b, i	X c	X	
Safety Follow-up Contact							X b			

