g For subjects treated at the hospital/study center only.

- h The subject will be observed for a minimum of 2 hours after icatibant administration. If after the completion of the assessments scheduled for 2 hours post-treatment, the subject's symptoms are absent or mild, no further Day 1 assessments are required. If the subject's symptoms at 2 hours post-treatment are moderate, severe, or very severe, the subject will be assessed every 2 hours until the subject's symptoms are absent or mild.
- i Injection site reaction will be recorded (1 hour [ $\pm 10$  minutes] post dose and 2 [ $\pm 0.5$ ] hours post dose, and every 2 [ $\pm 0.5$ ] hours until injection site reaction is mild or absent (if the subject's injection site reaction is not mild or absent at 2 hours post dose)

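### The SAP omits the caregiver symptom-score analyses promised in protocol 10.7 for repeat attacks, so home-treated attacks get no symptom-score result, yet SAP 8.2 declares no change

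*SAP*

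**What the plan says.** **Protocol.** Section 10.7 has the home healthcare provider or caregiver score symptoms at every repeat icatibant-treated attack. It then makes two commitments:

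- "A tabular summary of the average caregiver-reported symptom scores and the change from baseline in the average caregiver-reported symptom scores will be presented", broken down by stratification group and number of the repeat attack.
- "For individual caregiver-reported symptom scores, a shift table from baseline will be presented for each post-treatment time point".

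Section 7.11.1.2 gives these raters the same 5-point scale and symptom lists as the investigator. Section 7.11.4.2 also has them record when improvement was first noted.

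**SAP.** Section 7.8 states: "Efficacy will be assessed using data from the investigator symptom score, FPS-R and FLACC". Section 6.3 describes the same three instruments and no other. The SAP's own schedule for repeat attacks (10.3.3) nevertheless has a row for "Home Healthcare Provider or Parent/Legal Guardian/Caregiver Assessment of HAE Symptoms", before dosing and at 1, 2 and 6–8 hours. Sections 7.2 and 7.8 present repeat exposures by who gave the dose (site personnel, or home provider, patient or caregiver) and overall. Section 8.2 says that the analyses do not differ from those in the protocol.

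**Who scores where.** Protocol 8.4.2.1: "The investigator will assess HAE symptoms using the Investigator Symptom Score if the subject is treated at the hospital/study center". In SAP 10.3.3, footnote g to the investigator row reads: "For subjects treated at the hospital/study center only".

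**The concern.** Efficacy after repeated exposures is one of the study's other objectives (protocol 2.2, SAP 3.2), and home treatment is allowed for exactly those exposures. When a repeat attack is treated at home, the caregiver or home-provider score is the only symptom score scheduled. If the SAP does not analyse it, the attack drops out of the symptom-score results.

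A reader would not see this. The tables carry a caregiver-administration column and an overall column, so the overall column looks as if it covers all repeat attacks. SAP 8.2 also assures the reader that nothing promised in the protocol was dropped.

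**Working it through.** The plan gives no figure to reproduce. The check compares commitments with planned outputs.

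**1. Promised against planned, repeat attacks**

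| Protocol 10.7, caregiver score | In SAP 7.8 or Appendix I |
|---|---|
| Average score and change from baseline | Not planned |
| Individual-symptom shift from baseline, each post-treatment time point | Not planned |

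Promised output types: 2. Planned: 0.

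**2. Symptom-score outputs in SAP Appendix I that cover exposures 2 and 3**

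- Tables 14.2.1.2, 14.2.2.2, 14.2.3.2, 14.2.4.2, 14.2.4.4, 14.2.4.6, 14.2.4.8: 7
- Figures 14.2.1.2, 14.2.2.2, 14.2.3.2: 3
- Listing 16.2.6.1: 1

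Total 7 + 3 + 1 = 11. All 11 carry the investigator as rater in their titles; 0 name the caregiver.

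**3. Which score exists for which attack** (protocol 8.4.2.1; SAP 10.3.3)

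| Place of treatment | Investigator score | Home provider or caregiver score |
|---|---|---|
| Site | Yes | Yes |
| Home | No | Yes |

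The SAP analyses only the first score column. A home-treated attack therefore contributes nothing to the 11 outputs, and the overall column for exposures 2 and 3 rests on site-treated attacks. For site-treated attacks the parallel caregiver score also goes unused.

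**4. Possible scale.** Protocol 4.1.3.2 aims for at least 10 adolescents treated 3 times. Each has 2 treatments after the first, so there are at least 10 × 2 = 20 repeat treated attacks. The share treated at home is not given. As an assumed range:

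- 0% at home: 20 × 0 = 0 attacks without a symptom-score result
- 50%: 20 × 0.5 = 10
- 100%: 20 × 1 = 20

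**5. Initial symptom relief.** Protocol 7.11.4.2 has the home provider or caregiver record this time. SAP 7.8.4 and listing 16.2.6.4 name only the investigator, so the SAP does not say whether home-recorded times are used.

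**The case against.** The strongest reply is that *investigator symptom score* is simply the SAP's name for the instrument, and that caregiver scores are meant to feed the same tables. Both raters use one scale, and a caregiver-administration column would be largely empty without home scores. The SAP's titles are also loose: section 7.9.2 lets caregivers evaluate injection-site reactions, yet listing 16.2.7.6 is titled as assessed by the investigator.

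This does not hold on the text. Protocol 10.7 treats investigator-reported and caregiver-reported scores as separate and assigns each its own analyses. SAP 6.3.1 says that the investigator does the scoring. At the site two raters score the same attack, and no rule says which score would enter a table. Pooling the raters would itself be an undeclared change. The loose listing title shows that a title alone proves little, but the case rests on sections 6.3, 7.8 and footnote g as well. Output 14.2.9, a general listing of efficacy results, is not restricted by rater, but it cannot replace a promised summary or shift table.

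Several limits do stand:

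- The omitted analyses are descriptive and serve an *other* objective in a single-arm study without hypothesis tests.
- The protocol promises no time-to-relief analysis of caregiver scores and no analysis of recorded initial-relief time, so the initial-relief point is a clarification.
- FPS-R pain and rescue-medication use still cover home-treated attacks, as does initial relief if home-recorded times are used.
- Who gave the dose is not the same as where it was given, so the caregiver-administration column need not be empty.

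**Conclusion.** The concern holds. Two analyses promised in the current protocol are missing from the SAP, and the statement in SAP 8.2 is inaccurate. As written, home-treated repeat attacks have no symptom-score result, and the overall investigator-score results for exposures 2 and 3 describe site-treated attacks only.

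In outputs, the size is 0 of 2 promised caregiver types planned and 11 of 11 named symptom-score outputs investigator-rated. In attacks, it cannot be fixed from the documents: 0 to 20 of the minimum 20, depending on an unstated home-treated share. The conclusion assumes that the SAP means what it says about the rater and that scores are collected as scheduled. PK, safety and initial-exposure efficacy results are unaffected. The matter should be fixed before the final analysis, but it does not threaten the study's main conclusions.

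**What to change.** 1. Add to SAP 7.8 and Appendix I the two protocol 10.7 outputs for exposures 2 and 3 (average caregiver score with change from baseline; individual-symptom shift tables), plus a caregiver-score listing. Label each by rater.
2. With caregiver scores shown separately, footnote the overall column of the investigator-score tables for exposures 2 and 3 as covering site-treated attacks only.
3. In SAP 7.8.4 and listing 16.2.6.4, include initial-relief times recorded by the home provider or caregiver, and identify the rater.
4. Correct SAP 8.2 so that any protocol analysis still left out is named with a reason.

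A supportive time-to-relief analysis of caregiver scores is optional; the protocol does not promise it.

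The cost is SAP text, two descriptive table types and one listing, with no new assessments. Lay and professional raters may score differently, so the results should not be pooled. The caregiver score came in with Amendment 4, so any repeat attack treated before then has none, and the new tables should state their denominators.

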^a All evaluations and sample collections must be performed at the hospital/study center within 6 months prior to treatment if a repeat attack does not occur within 6 months. If a second “baseline” visit is conducted due to lack of repeat attacks, one of the monthly phone calls may overlap with the onsite visit. In this case, a monthly call would not be necessary.

^b These assessments may be conducted by telephone contact.

^c If a subsequent attack occurs within 3 days of the Day 8 follow-up visit for the previous attack, the visits for Day 1 (of the subsequent icatibant-treated attack) and Day 8 (of the prior icatibant-treated attack) will be combined. If a subsequent attack occurs within 7 days of the Day 90 follow-up visit for the previous attack, the visits for Day 8 (of the subsequent icatibant-treated attack) and Day 90 (of the prior icatibant-treated attack) will be combined.

^d For subjects who have expressed an interest in self-administering or having a parent/legal guardian/caregiver administer icatibant in the home.

^e For subsequent attacks, study drug may be administered by study site personnel at the hospital/study center or by qualified home healthcare personnel at the subject’s home. Alternatively, a parent/legal guardian/caregiver will be allowed to administer or the subject (under the supervision of a parent/legal guardian/caregiver) will be allowed to self-administer the investigational product after having received appropriate training. For all subsequent laryngeal attacks, subjects should be advised to seek medical attention in an appropriate healthcare facility immediately following treatment with icatibant.

^f If after the completion of the assessments scheduled for 2 hours post-treatment, the subject’s pain is absent, no further Day 1 assessments are required. If the subject’s pain at 2 hours post-treatment is NOT absent, the subject will be assessed every 2 hours until pain is absent.

^g For subjects treated at the hospital/study center only.

^h The subject will be observed for a minimum of 2 hours after icatibant administration. If after the completion of the assessments scheduled for 2 hours post-treatment, the subject’s symptoms are absent or mild, no further Day 1 assessments are required. If the subject’s symptoms at 2 hours post-treatment are moderate, severe, or very severe, the subject will be assessed every 2 hours until the subject’s symptoms are absent or mild.

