Time to onset of symptom relief for individual symptom is defined as duration of time in hours from study drug administration to the earliest time post-treatment when the specific symptom is either mild or absent. Subjects not achieving the relief for individual symptom criteria will be censored at the time of their last symptom assessment. Time to onset of symptom relief for individual symptoms will be summarized using the Kaplan-Meier method. Subjects with the individual symptom as mild or absent at pretreatment will be excluded from the analysis on that symptom.

Analyses on investigator symptom score will be performed for the initial icatibant exposure and both subsequent exposures.

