**8.2 Changes from the Analyses Planned in the Protocol**

There was no change from the analyses planned in the protocol.

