#### 10.2.10 Deriving Time to First Use of Rescue Medication for Subjects with Missing Time to Onset of Symptom Relief

Subjects with missing pretreatment symptom assessments would be excluded from the time to onset of symptom relief analysis. If a subject was excluded from the time to onset of symptom relief analysis, but received a rescue medication within 48+4 hours after an on-study icatibant exposure, then the time between the icatibant treatment and the first rescue treatment use would be considered as time to first use of rescue medication.

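### The SAP drops, without declaring it, the caregiver symptom-score tables that the protocol plans for repeat attacks, so home-treated attacks have no symptom-score data in any named table

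*SAP*

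**What the plan says.** **Protocol, collection.** At a repeat attack the investigator's score is taken "For subjects treated at the hospital/study center only" (Appendix 3, note g; SAP 10.3.3 repeats the note, and Protocol 7.11.1.1 agrees). The parent or caregiver completes the caregiver version of the "Symptom Score if the subject is treated at either the hospital/study site or at home" (Protocol 8.4.2.1). A home healthcare provider scores if present at a home treatment.

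**Protocol, analysis.** Section 10.7 plans a table of the mean caregiver score and its movement from baseline at repeat attacks. It adds: "For individual caregiver-reported symptom scores, a shift table from baseline will be presented for each post-treatment time point".

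**SAP, efficacy.** Section 7.8 says "Efficacy will be assessed using data from the investigator symptom score, FPS-R and FLACC". Section 7.8.1 says "Analyses on investigator symptom score will be performed for the initial icatibant exposure and both subsequent exposures". Section 7.2 says that "for the subsequent icatibant exposures, the analyses will be presented by the administration type", meaning study site personnel (HCP Administration) against home providers, patients and families (Caregiver Administration).

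**SAP, exclusions and changes.** Section 10.2.10 says "Subjects with missing pretreatment symptom assessments would be excluded from the time to onset of symptom relief analysis". Section 8.2 says "There was no change from the analyses planned in the protocol".

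**The concern.** The protocol collects a caregiver score at every repeat attack and says how it will be tabulated. The SAP keeps the collection in its schedule but names no output for it, while asserting that nothing changed.

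Efficacy after repeated exposure is a stated objective (Protocol 2.2), and the SAP chooses to show it by who administered the dose. On the symptom score, that comparison cannot be filled for home treatment from the source that the SAP names. A reader of the report could take a repeat-attack relief result as covering all repeat attacks when it covers only those treated at a site.

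There is a secondary consequence. Under Protocol 7.17.1.1, worsening of a treated attack is attributed to the disease and is not an adverse event unless serious. The symptom score is therefore where item-level worsening would be tabulated, and for home-treated attacks no named table does so.

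**Working it through.** No sample-size or test calculation bears on this point. The check sets plan against plan and counts outputs.

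1. **What the protocol plans.** Section 10.7 gives 2 table types for the caregiver score at repeat attacks.

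2. **What the SAP names for exposures 2 and 3** (Appendix I):
   - Tables: 14.2.1.2, 14.2.2.2, 14.2.3.2, 14.2.4.2, 14.2.4.4, 14.2.4.6 and 14.2.4.8, which is 7.
   - Figures: 14.2.1.2, 14.2.2.2 and 14.2.3.2, which is 3.
   - Listing: 16.2.6.1, which is 1.
   - Total: 7 + 3 + 1 = 11, all titled as investigator-assessed. Outputs named for the caregiver score: 0.

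3. **What the SAP declares as changed.** Section 8.2 declares nothing.

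4. **Whether the SAP simply predates the caregiver score.** It does not. The protocol's change summary shows that the caregiver paragraph in 10.7 and home dosing both came in with Amendment 4. The SAP reflects that amendment: its schedule (10.3.3) has a caregiver-assessment row, and it splits repeat exposures by administration type.

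5. **Whether the promised split can be filled.** An attack treated at home has no investigator score. The Caregiver Administration column of an investigator-score table is therefore empty unless a caregiver or the subject injects at the site. SAP 9.2.1 does not repair this, because it imputes single missing items only when the assessment was performed.

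6. **Effect on time to onset of relief.** With no pretreatment investigator assessment, a home-treated attack meets the exclusion in SAP 10.2.10. It drops out of the endpoint that SAP 7.8.1 calls primary for efficacy, and SAP 7.8.1 does not say that the result is limited to site-treated attacks.

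7. **What is still reported for home-treated attacks.** FPS-R pain (14.2.5.2, 14.2.5.4, 14.2.5.6), rescue medication (14.1.4.3, 14.1.4.6, and 14.2.7.2 if at least 5 subjects used it before relief), adverse and serious adverse events, and injection site reactions. Time of first overall improvement may be in 14.2.8.2: Protocol 7.11.4.2 has home raters record it, but SAP 7.8.4 names only the investigator. None of these tabulates worsening of individual non-pain symptoms.

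8. **How many attacks.** At least 10 adolescents are to be treated 3 times (Protocol 4.1.3.2). That gives 10 × 2 = 20 repeat doses as the planned minimum, all for attacks. Neither document states how many are given at home, so the range is 0 to 20 of 20.

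**The case against.** **The titles may be loose.** Listing 16.2.7.6 is labelled as investigator-assessed, yet SAP 7.9.2 lets caregivers evaluate injection site reactions. The caregiver score uses the same scale and items as the investigator's. The authors may have meant home scores to feed the tables labelled investigator, which would explain the administration-type split. This is possible, but SAP 6.3.1, 7.8 and 7.8.1 all say investigator, and no text substitutes one rater for the other. If substitution was intended, raters would be mixed without a label, and the SAP would still need to say so.

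**Home worsening is not invisible.** Protocol 7.17.1.1 sends clinically relevant worsening to its own CRF page. Families must call if there is no improvement and they think more treatment is needed (6.7), and they contact the site at 6 to 8 hours (8.4.2.1). Subjects with laryngeal attacks are advised to seek care at once. SAP 10.2.14 counts non-ongoing drugs given for HAE or swelling in the 48+4 hour window as rescue. Listings 14.2.9 and 16.2.4.5 may carry some of these data, though their content is not stated. All of this stands. It limits the point to the absence of a named table of item-level, non-pain worsening.

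**The stakes are limited.** The defined secondary endpoints are investigator- and subject-reported, the caregiver score is descriptive, and repeat-attack efficacy is listed among the other objectives. PK and first-attack efficacy are untouched. This also stands, and it bears on priority rather than on whether the SAP is wrong.

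**Conclusion.** The point holds. The SAP omits two protocol-planned tables, its statement of no change is incorrect, and its administration-type display of the investigator score cannot be populated for home-treated attacks. This should be corrected; it does not threaten the study's main results.

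The size is 0 to 20 of at least 20 repeat doses, depending on how many were given at home. The omission of the tables does not depend on that number, because parents also score at the site. The empty column and the exclusion from time to onset of relief do require some home treatment, and they assume that the SAP is followed as written.

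Three stronger readings are tempting, and the documents do not support them:

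- *Harm or lack of benefit at home goes unreported.* Adverse events, serious events, pain, rescue use and injection site reactions are all tabulated, and overall improvement may be. How many drug effects might be put down to the attack cannot be estimated.
- *The caregiver score would give a single-rater comparison of site and home.* Protocol 10.7 pools home healthcare providers with parents, and the scoring training in 8.4.1 is described for families interested in home dosing.
- *A new table of any worsened symptom is needed.* The protocol plans none. Using investigator scores at site and caregiver scores at home would confound rater with setting.

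**What to change.** 1. In SAP 7.8 and Appendix I, restore for exposures 2 and 3 the caregiver mean score, its change from baseline and the individual-symptom shift table. Add a listing. Label each by rater: home healthcare provider, or parent/caregiver.
2. In SAP 7.8.1, state that investigator-score analyses at exposures 2 and 3 cover site-treated attacks only, and report how many attacks have no investigator score.
3. Correct SAP 8.2, or declare and justify the omission there.

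The cost is SAP text, a little programming, and caregiver and investigator ratings that must be read separately. No protocol amendment or new data are needed, and the adverse event definition stays as it is. One limit remains: scoring may stop at 2 hours once symptoms are mild or absent (Appendix 3, note h), so later worsening may still be missed.
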